8.2.2 Secondary endpoints

- OS is defined as the time from first infusion of ATO to death, regardless of the cause
- FFS is defined as related death, progression, or initiation of a new systemic treatment for chronic GvHD
- PFS is defined as survival with no evidence of relapse or progression of the original disease

- Corticosteroids dosage and percentage of reduction in corticosteroids dosage at 6 and 12 months after diagnosis of chronic GvHD and treatment with ATO as first line treatment
- Quality of life parameters using FACT-BMT and Lee Symptom Scale scores at 6 and 14 weeks, 6, 9 and 12 months after first infusion of ATO
- Tolerability and safety of ATO

9. INVESTIGATIONAL PLAN

9.1 OVERALL STUDY DESIGN AND PLAN

[figure not shown]
The study GMED16-001 is a prospective, national, multicenter, non-randomized phase II study that will include a total number of 24 patients.

The duration of participation planned is as follows:

- Duration of recruitment: 34 months
- Study duration for a considered patient: 12 months
- Total duration of the study: 46 months

Several visits are scheduled in the study as follows:

- At the time of diagnosis for the screening visit
- Follow-up visits to be performed every week during ATO treatment
- Follow-up visits to be performed every 2 weeks from second to third month of ATO treatment
- Follow-up visits to be performed every month from the fourth to sixth month of ATO treatment
- Follow-up visits to be performed every 3 months: at 9 months and 12 months (final visit)

Arsenic trioxide is administrated either via the marketed product named TRISENOX® or the investigational medicinal product named ARSCIMED®.

9.2 SELECTION OF STUDY POPULATION

9.2.1 Inclusion criteria

Patients will be eligible for inclusion in this study if the patient met all the following criteria:

- Adult patients (≥ 18 years) who have received a first allogeneic stem cell transplantation for a hematological disease (any source of hematopoietic stem cells is authorized; any category of conditioning regimen prior to allo-SCT is authorized; any type of stem cell donors is authorized)
- Confirmed diagnosis of first episode of chronic GvHD requiring systemic immunosuppressive therapy (any prior GvHD prophylaxis previously used is accepted). Chronic GvHD diagnosis is defined according to the National Institutes of Health (NIH) Working Group Consensus.
- Signed informed consent
- Absence of contra-indications to the use of ATO
- Subjects affiliated with an appropriate social security system
- Men must use a medically acceptable method of contraception throughout the treatment period and for at least 4 months and 10 days following the last treatment administration
- Women who are of childbearing potential must have a negative serum pregnancy test and agree to use a medically acceptable method of contraception throughout the study and for 3 months following the end of the study
- Patient not participating or not having participated in a clinical study in the 30 days prior to his/her inclusion in the study

9.2.2 Exclusion criteria

Patients fulfilling ONE or MORE of the following criteria will not be included in the study:

- Patient developing acute GvHD (whether early or “late onset” form)

- Patients developing overlap GvHD as defined by the 2015 NIH Working Group Consensus (presence of one or more acute GvHD manifestation in a patient with a diagnosis of chronic GvHD)
- A “mild” form of chronic GvHD not requiring systemic immunosuppressive therapy
- A “moderate” form of chronic GvHD limited to one organ site not requiring systemic immunosuppressive therapy
- Patient receiving mycophenolate mofetil
- Second allogeneic stem cell transplant
- Severe cardiac diseases (congestive heart failure (NYHA class III), recent myocardial infarction (in the past 6 months before the inclusion), histories of unexplained syncope, ...)
- Significant arrhythmias, EKG abnormalities
 - Congenital QT syndromes
 - History or presence of significant ventricular or atrial tachyarrhythmia
 - Clinically significant resting bradycardia (<50 beats per minutes)
 - QTc > 450 msec for men and > 470 msec for women on screening EKG
 - Right bundle branch block plus left anterior hemiblock, bifascicular block
- Central or peripheral neuropathy
- Neutrophils < $0.5 \times 10^9/L$
- Platelets < $50 \times 10^9/L$
- Potassium $\leq 4 \text{ mEq/l}$
- Magnesium $\leq 1.8 \text{ mg/dl}$
- Calcium $\leq 2.15 \text{ mmol/l}$
- Hepatic impairment due to a suspected or proven liver damage, other than direct hepatic cGvHD involvement
- PT < 50%
- Renal impairment (creatinine $\geq 100 \mu\text{mol/l}$)
- Uncontrolled systemic infection which in the opinion of the investigator is associated with an increased risk of the patients death within 1 month after the start of therapy
- Severe neurological or psychiatric disorders

- Denied informed consent
- Pregnancy
- Women breastfeeding at selection and throughout the treatment period

9.3 TREATMENTS

9.3.1 Treatments administered

Arsenic trioxide (ATO) is administrated either via a marketed product, i.e. TRISENOX®, or an Investigational Medicinal Product, i.e. ARSCIMED®.

TRISENOX® was administered to patients from the start of the clinical trial. ARSCIMED® will be administered to patients included in the clinical trial after approval from the ANSM for its use in this clinical trial. Patients under TRISENOX® treatment will not switch to ARSCIMED® treatment nor vice versa.

- All patients already included in the trial and who received TRISENOX® will continue with TRISENOX® until completion of their participation in the clinical trial.
- All patients recruited after this amendment has been approved will receive ARSCIMED® only and not TRISENOX®.

TRISENOX® and ARSCIMED® have the same active substance, excipients, dosage form and route of administration (Summary of Product Characteristics (Trisenox)) and Investigator brochure (ARSCIMED®) for details) and are considered equivalent. The decision in switching to ARSCIMED® during the clinical trial is based on the fact that the availability of ARSCIMED®, treatment being developed by MEDSENIC in the population included in this trial, will avoid repeated and further impact on recruitment in the study related to any further supply disruptions of TRISENOX®, as it occurred in 2014 and again in 2017.

Both formulations (TRISENOX® and ARSCIMED®) are adjusted to pH 8 with dilute hydrochloric acid. Whereas TRISENOX® is manufactured by TEVA and supplied as a glass ampoule; ARSCIMED® is manufactured by IRPF¹ -Toulouse and supplied as a glass vial. Further information on ARSCIMED® is available in the Investigational Medical Product Dossier of this product.

9.3.2 Identity of Investigational Product(s)

The investigational medication has the following characteristics:

- ATC code: LOIXX27
- Pharmacotherapeutic group: other antineoplastic agents
- Form/Presentation: concentrate for solution for intravenous infusion / 1 mg/1 mL / 10 mL
- Excipients: sodium hydroxide, hydrochloric acid as pH adjuster and water for injections

9.3.3 Administration

- 0, 15 mg/kg/infusion on days 1 to 5 (first week), 3 times per week during the second week (for example, days 8, 10 and 12), 2 times per week during the third week (for example, days 15 and 17) and one time during the fourth week (for example, day 24), in addition to Ciclosporin A (if relevant) and corticosteroids. The latter four weeks represent one cycle of 11 administrations.
- Must be administered intravenously over 1-2 hours. The infusion duration may be extended up to 4 hours if vasomotor reactions are observed. A central venous catheter is not required. Patients must be hospitalized at the beginning of treatment due to ensure adequate monitoring.
- Aseptic technique must be strictly observed throughout handling of ATO since no preservative is present.
- Must be diluted with 100 to 250 mL of glucose 50 mg/mL (5%) solution for injection or sodium chloride 9 mg/mL (0.9%) solution for injection immediately after withdrawal from the ampoule for single use only. Unused

portions of each ampoule must be discarded properly. Unused portions for later administration must not be saved.

- Must not be mixed with or concomitantly administered in the same intravenous line with other medicinal products.
- The diluted solution must be clear and colorless. All parenteral solutions must be inspected visually for particulate matter and discoloration prior to administration. The preparation must not be used if foreign particulate matter is present.
- Should be administered within 10 days of starting prednisone at 1 mg/kg/day for cGvHD treatment. Treatment with persistent prednisone (or equivalent) at doses lower than 1 mg/kg/day at the time of enrollment is allowed (i.e patient was treated for acute GvHD with prednisone and developed evolving chronic GvHD).
- A delay of 8 weeks to a maximum of 11 weeks (from the first infusion of ATO) will be observed between the two cycles of ATO therapy.

9.3.4 Method of Assigning Patients to Treatments Groups

Not Applicable

9.3.5 Blinding

Not Applicable

9.3.6 Prior and Concomitant Therapy

9.3.6.1 Ciclosporin A

- Ciclosporin A will be delivered using local standard criteria, (if relevant).

However:

- Ciclosporin level should lie within the therapeutic range (i.e. 200-400 ng/mL): to harmonize CSA target levels
- Ciclosporin-induced renal insufficiency should lead to dose adjustment and even temporary withdrawal of the drug

- Suggested guidelines for initial dose of Ciclosporin A:

Oral administration of Ciclosporin should continue for patients who are being treated with Ciclosporin at the time of enrolment, or if it is relevant. the administration should commence initially at 6mg/kg daily.

- Monitoring of Ciclosporin level:

- Concentrations of Ciclosporin in the plasma may be monitored at the discretion of the investigator. Dose adjustments may be made to maintain Ciclosporin concentrations at 200-400 ng/ml. Monitoring may be especially helpful in patients with renal impairment and in patients being treated with medications that may affect the concentration of Ciclosporin.
- Medications that could increase the concentration of Ciclosporin include diltiazem, nicardipine, verapamil, metoclopramide, ketoconazole, fluconazole, itraconazole, erythromycin and methylprednisolone.
- Medications that could decrease the concentration of Ciclosporin include rifampycin, phenytoin, phenobarbital and carbamazepine.

- Deviations from guidelines for administration of Ciclosporin

Deviations from the above guidelines may be made at the discretion of the investigator in consultation with the transplant centre. Toxicity associated with the

administration of Ciclosporin may require dose adjustments, which should be managed according to individual transplant centre practice.

9.3.6.2 Prednisone

- The initial dose of prednisone is 1.0 mg/kg/day, this dose should be maintained for 2 weeks, after which a tapering schedule should commence up until response assessment at 6 weeks, after which treatment is as follows:
 - CR: continue tapering of Prednisone dose (see Table below)
 - No CR: maintain Prednisone dose at 1 mg/kg/day on alternate days or 0.5 mg/kg/day every day

Usual prevention of steroid-induced gastro-intestinal (GI) side effect should be given (omeprazole or other drugs, according to local practice).

- The investigator will determine the regimen for administration of prednisone after enrolment in the study. The following taper schedule is given as a general guideline:

Prednisone Taper Schedule

Week	Dose (mg/kg actual body weight/day)
0	1.0 qod
2	0.75 qod
4	0.65 qod
6	0.50 qod (if CR, continued tapering of corticosteroids dose) 0.50 qod (if No CR, maintain this dose until resolution of all reversible clinical manifestations or adjust the required dose)

8	0.40 qod
10	0.30 qod
12	0.20 qod
14	0.15 qod
20	0.0

- The investigator should examine the patient before each reduction in the dose of prednisone. If there is exacerbation or recurrence of chronic GvHD at any step of the taper, the dose of prednisone should be increased by 2 levels with daily administration for 2-4 weeks, followed by resumption of alternate day administration. Prednisone may be discontinued after 2 weeks of treatment at a dose of 0.15 mg/kg every other day. Qod prednisone dosing is not required, and the use of qod dosing is at the discretion of the investigator. It is suggested, but not required, that patients taper off steroids before tapering of other immunosuppressive medications.
- Toxicity associated with the administration of prednisone should be managed according to individual transplant center practice.

9.3.6.3 Preventive treatments for infections

- Antibiotic prophylaxis for prevention of Pneumocystis pneumonia and infections with encapsulated organisms must be given to all patients until 6 months after discontinuation of all systemic immunosuppressive treatment. Suggested antibiotic regimens are: Trimethoprim/Sulfamethoxazole DS I tab PO qMWF, or if sulfa allergic, Atovaquone 1500 mg PO qMWF or Pentamidine 300 mg inhaled q4 weeks. Additional prophylactic antibiotics are at the discretion of the physician.

- Prophylactic antiviral and antifungal medications must also be given until the steroid dose is stable < 0.15 mg/kg/day. All patients who are at risk of CMV infection should be monitored for occult CMV infection, and appropriate treatment should be instituted per institutional practice. Populations at risk of CMV infection include all CMV seropositive patients, all CMV-seronegative patients with CMV-seropositive donors, and all patients receiving blood product transfusions from CMV-seropositive donors.
- Antifungal prophylaxis: No specific antifungal prophylaxis is recommended. In case it is the routine policy of a centre to give an antifungal prophylaxis in patients with chronic GvHD (i.e., fluconazole, oral amphotericin B, itraconazole, posaconazole or other drugs for which there are published data of controlled trials showing the antifungal prophylaxis of this drug in allo-SCT patients), it is required that this policy is being documented in the CRF and the same policy be applied to all the patients included in the centre.
- In all cases, physicians can refer to the recommendations made by the European Conference on Infections in Leukemia (ECIL). The full version is available on the website of the EBMT:
<https://www.ebmt.org/Contents/Resources/Library/ECIL/Pages/ECIL.aspx>
- All treatments given for prevention of infectious complications must be reported in the electronic CRF of the study.

9.3.6.4 Prohibited concomitant treatments

- Patient receiving mycophenolate mofetil
- Any other investigational study drugs than ATO

9.4 EFFICACY AND SAFETY VARIABLES

9.4.1 Efficacy and Safety Measurements Assessed and Schedule of Assessments

Patients will undergo the procedures and examinations which must be performed as shown in the following flow chart:

	Selection (V1) (10 days before ATO treatment)	During ATO treatment (1st and 2nd cycles)	Every 2 weeks (from M2 to M3) ± 5 days	Every month (M4, M5, M6) ± 5 days	At 6 and 14 weeks and every 3 months (M6, M9, M12) ± 5 days	Study drop- out ± 5 days
Information and patient consent	*					
Inclusion/exclusion criteria check	*					
Socio-demographics	*					
Concomitant diseases	*					
Recipient, Donor and Transplant characteristics ¹⁰	*					
Diagnosis & Scoring of chronic GvHD	*					
Chronic GvHD activity assessment form A	*				*	*
Chronic GvHD activity assessment form B	*				*	*
Lee Symptom scale	*				*	*
FACT-BMT	*				*	*
Physical examination	*	*1	*	*	*	*
EKG – QTc1 measurement	*	*1	*			
Hematology3	*	*9	*	*	*	*
Biochemistry4	*	*2/9	*	*	*	*
Coagulation test5	*	*9	*	*	*	*
Infectious disease surveillance	*	*2		*	*	*
Serum immunoglobulin level	*			*	*	*
Autoantibodies (AAN, ANCA)	*	*2		*	*	*
Serum pregnancy test	*					

Immunological evaluation (Saint-Antoine)	*	*			*	*
Pharmacokinetic evaluation		* ⁶				
Pulmonary function test (FEV1)	*				*	*
Chest x-ray	*					
Cutaneous biopsy (if relevant)	*					
ATO treatment (date, dose, reason of change)		*				
Response to treatment					*	
Associated treatment(s) ⁸	* ⁷	*	*	*	*	*
Adverse event(s)		*	*	*	*	*

¹ During ATO treatment, must be performed daily before each ATO administration.

² Must be performed weekly.

³ CBC included leucocytes, neutrophils, lymphocytes, monocytes, and eosinophils counts, hemoglobin and platelets.

⁴ Biochemistry included measurement of glycaemia⁹, creatinine¹, uric acid, calcium¹, potassium¹, magnesium¹, total protein, albumin, total bilirubin, alkaline phosphatases, SGOT⁹, SGPT⁹, and LDH.

⁵ Prothrombin time [PT], activated partial thromboplastin time [APTT].

⁶ Pharmacokinetic evaluation: the samples must be performed before each administration at D2, D3, D4, D5, D8, D12, D17 and D24 of cycle 1 and cycle 2 (if applicable).

⁷ History of GvHD prophylaxis : documentation of any associated treatments and topical therapy since graft for acute GvHD or progressive form of cGvHD treated by corticotherapy < 1 mg/kg/day, whenever possible given collected clinical history

⁸ Documentation of any associated treatments and topical therapy for chronic GvHD (including glucocorticoid creams, topical tacrolimus, oral beclomethasone or budesonide, topical azathioprine and ophthalmic glucocorticoids...)

⁹ Must be performed twice a week.

10 Documentation on the diagnosis of hemopathy requiring transplant and DLI modality.

9.5 DATA QUALITY ASSURANCE

9.5.1 GOOD CLINICAL PRACTICE

The study will be performed according to the Guidelines for Good Clinical Practice (ICH Harmonized Tripartite Guideline for Good Clinical Practice, (17.01.1997)).

The investigator will be thoroughly familiar with the appropriate use of the study drug as described in the protocol and SPC. Essential clinical documents will be maintained to demonstrate the validity of the study and the integrity of the data collected. A trial master file should be established at the beginning of the study, maintained for the duration of the study and retained according to the appropriate regulations.

9.5.2 AUDITING

To guarantee a high quality of treatment for the patients within the present study, the sponsor will insure that the participating centres fulfill the following criteria:

- Fulfilling of legal requirements - experience of the principle investigator of the entire study and the respective centre with respect to study conduct
- International Conference on Harmonization (ICH)/GCP knowledge and certifications

9.5.3 MONITORING

Regular monitoring is an essential part of the study conduct. It will be performed by the Sponsor of the study. After the initiation visit, the frequency of monitoring visits will depend on the course of the study, and recruitment. It is the monitor's responsibility to make the local investigators and all the staff who is involved into the study or the care of the patients familiar with the protocol.

During the course of the study, the monitor will control the progress of the study, the commitment to the protocol, the documentation and careful usage of the study medication, and the maintenance of GCP guidelines and legal obligations. Problems as well as changes in reported data will be worked out in collaboration with the local investigator, who is obliged to cooperate with the monitor and to allow access to the patients' charts. Source data verification is performed by the monitor. This protocol is classified as a "D" risk level estimated for the patients (Phase 11= very high risk predictable).

Inclusion criteria will be verified in 100% of patients. The monitor will have to respect that the data she/he comes into contact with are highly confidential. A monitoring report will be provided for each visit.

9.5.4 DATA MANAGEMENT

The coding and data control for the exploitation of results of the study will be conducted by the Contract research Organization (CRO) in charge of the study, FOVEA (RueilMalmaison, France), according to its standard operating procedures, ICH guidelines, and under the supervision of the Sponsor.

9.5.4.1 Data entry

All study data will be recorded and stored in a computerized database within the CRO, under the supervision of the Data Manager and under appropriate procedures. The data are available within the system to the Sponsor as soon as they are entered in the e-CRF.

9.5.4.2 Consistency checks

Procedures for control of electronic data (Data Computer Management) will be defined to ensure the validity of information gathered as part of this study. They will cover all of the data and will aim to highlight abnormalities as missing data or inconsistent data.

These controls will be fully described in a manual of Data Management and will be implemented in the e-CRF. The computerized handling of the data by the Sponsor may generate additional requests (discrepancy resolution forms) to which the Investigator is obliged to respond by confirming or modifying the data questioned. The requests with their responses will be managed through the e-CRF.

9.5.4.3 Data coding

The AES will be coded using the Medical Dictionary for Regulatory Activities (MedDRA), while previous treatments will be coded using the World Health Organization (WHO) dictionary according to anatomic-therapeutic-chemical classification (ATC).

12.4 STATISTICAL ANALYSIS METHODS PLANNED IN THE PROTOCOL AND DETERMINATION OF SAMPLE SIZE

12.4.3 Statistical and Analytical Plans

12.4.3.1 General approaches

All continuous data will be summarized using the following statistics: n (non-missing sample size), mean, standard deviation, median, minimum (min) and maximum (max). All categorical/qualitative data will be presented using the frequency and the percentage of patients who are in the particular category. In general, all data will be listed, sorted by site, subject, and by visit number within subject. All summary tables will be annotated with the total population size relevant to that table/treatment, including any missing observation.

The mean and the standard deviation will be reported to one decimal place greater than the original data. Median, minimum and maximum will use the same number of decimal places as the original data. P-values ≥ 0.001 will be reported to 3 decimal places; p-values less than 0.001 will be reported as “<0.001”.

Type 1 error rate will be set at 0.05.

All statistical analyses will be conducted using SAS version 9.4.

12.4.3.2 Handling of Dropouts or Missing Data

Every effort will be made to keep the number of missing values for all parameters to a minimum. The number of missing values will be reported together with summary statistics for each variable.

Missing data on overall survival is assumed to be null as patient care after transplantation is very close. Any patient prematurely withdrawn or ending the study without the event of interest (progression, death) will be censored at his/her last information date.

Concerning the main endpoint (response at M6), the missing assessments will be fully discussed during the data review. The most plausible outcome (the clinically more relevant) will be used for the main analysis. Other methods of imputation (for example, worst

outcome: missing data=failure) could be used for sensitivity purpose, according to the final number of missing assessments.

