### **10.7. Calculation of the number of patients**

Based on results from the literature, the hypothesis for the primary endpoint is an improvement in response rate (CR and PR) at 6 months after the diagnosis of chronic GvHD and start of ATO from 60% to 85%. Using a one-step A'Hern procedure (A'Hern RP, 2001) (and anticipating a dropout rate around 10%), 24 (21+3) patients are needed. If the number of successful cases is 17 or more among the 21 patients, the hypothesis that the CR rate at 6 months is less than 60% is rejected with a target error rate of 0.05 (alpha probability). The beta probability in this case is 0.2.

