12.4.3.5 Determination of sample size

The aim of this study is to assess whether ATO allows improving response rate at 6 months after the diagnosis of chronic GVHD from 60% to 85%.

For the sample size calculation in this trial, an A'Hern one stage design has been used (ref 1).

- Let P_0 be the smallest response rate, if true, implies that the role of ATO is too low and therefore the present schedule does not warrant further investigation. In the present trial, P_0 has been taken as 60%.
- Let P_1 be the highest response rate which, if true, implies that the feasibility is sufficiently high and therefore the current schedule warrants further investigation in clinical trials. In the present trial, P_1 has been taken as 85%;
- Let α be the accepted probability of recommending for further investigation a regimen with a true discontinuation rate at least equal to P_0 . In the present trial, α has been taken as 0.05.
- Let β be the accepted probability of rejecting for further investigation a regimen with a true discontinuation rate less than P_1 . In the present trial, β has been taken as 0.20.

The required number of eligible patients is 21. To compensate for a dropout of 10%, 24 patients are planned to be included.

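### Missing month-6 responses enter the main analysis by open judgement at the data review, the missing-as-failure check is optional, and the rule conflicts with three other passages

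*SAP*

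**What the plan says.** SAP 12.4.3.2 states that missing M6 assessments will be discussed at the data review, and then: "The most plausible outcome (the clinically more relevant) will be used for the main analysis". It gives no criteria for plausibility, no list of assessors and no algorithm. The conservative alternative appears only as an example of what might be done: "outcome: missing data=failure) could be used for sensitivity purpose, according to the final number of missing assessments". It is not among the four sensitivity analyses in SAP 11.4.1.2 or the planned tables in SAP 14.2.2. The study has one group, and SAP 9.3.5 gives blinding as "Not Applicable".

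Three other passages bear on the same patients:

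- SAP 11.4.1.1 codes the primary variable as yes if the investigator judged a complete or partial response at M6, and as no in every other case.
- Protocol 10.4.1 says that dropout without follow-up information after a response does not cancel an efficacy success.
- Protocol 10.4.2 classes dropout after a toxic study-drug outcome, during primary treatment, as efficacy failure.

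Protocol 10.5, on missing data, gives no rule for a missing response.

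**The concern.** The primary result is a count in about two dozen patients, compared with a fixed 60%. If some of that count is supplied by judgement, made when earlier visits and other patients' outcomes can be known, the estimate cannot be reproduced from the SAP. The test also loses a defined error rate. The one analysis that would show how much depends on the judgement may never be run, because the choice to run it comes after the number missing is known. The unreconciled passages add a second problem: two analysts following the documents faithfully could classify the same patient differently.

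**Working it through.** **Inputs.** SAP 12.4.3.5: "P_0 has been taken as 60"%, "P_1 has been taken as 85"%, and "The required number of eligible patients is 21. To compensate for a dropout of 10%, 24 patients are planned to be included". SAP 12.4.3.1: "Type 1 error rate will be set at 0.05". Protocol 10.7: "The beta probability in this case is 0.2", with success declared at 17 or more responders of 21.

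**The plan's own design.** Let X be binomial.

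- P(X ≥ 17 | n = 21, p = 0.60) = 0.037
- P(X ≥ 17 | n = 21, p = 0.85) = 0.803
- 21 / 0.90 = 23.3, rounded up to 24

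The design figures reproduce.

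**The test the SAP specifies.** SAP 11.4.1.1 compares the lower bound of a two-sided 95% Clopper-Pearson interval with 60%. It prints rejection when the bound is lower than 60%; I read this as higher than, which is a separate matter. For r responders of N the lower bound is the 2.5% quantile of a Beta(r, N − r + 1) distribution. At N = 24:

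- 19/24: 57.8%, no rejection
- 20/24: 62.6%, rejection

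The cut-off is therefore 20 of 24. With nothing missing, type I error at 60% is P(X ≥ 20 | 24, 0.60) = 0.013, and power at 85% is 0.713.

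**How far judgement can move the test.** Suppose m of the 24 lack an M6 response, unrelated to outcome. If all are called responders, the observed patients must supply 20 − m, so the error is P(X ≥ 20 − m | 24 − m, 0.60). If all are called failures, it is P(X ≥ 20 | 24 − m, 0.60).

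| Missing m | All called responders | All called failures |
|---|---|---|
| 0 | 0.013 | 0.013 |
| 1 | 0.019 | 0.005 |
| 2 | 0.027 | 0.002 |
| 3 | 0.037 | 0.0003 |

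The documents do not give m. The range 0 to 3 is an assumption taken from the allowance of 24 − 21 = 3.

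**One data set, two conclusions.** Take 17 responders among 21 observed, with 3 missing.

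- All failures: 17/24 = 70.8%, lower bound 48.9%, no rejection.
- All responders: 17 + 3 = 20, and 20/24 = 83.3%, lower bound 62.6%, rejection.

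**The passages side by side.** Consider a patient who responds at week 14 and is then lost before M6. Protocol 10.4.1 points to success. SAP 11.4.1.1, read literally, gives non-response. SAP 12.4.3.2 leaves it to the meeting. If the loss followed a toxic outcome during primary treatment, Protocol 10.4.2 makes it a failure. No passage says which governs.

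**The case against.** The strongest reply is that judgement is less free, and matters less, than it looks.

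- *The analysis set limits it.* The full analysis set (SAP 11.1) already removes patients who did not complete the first cycle or lack a week-6 evaluation. Only losses between week 6 and M6 are imputed. This stands. A reader might infer that the planned 10% dropout is the number to be judged, but the documents do not say so.
- *The error rate survives.* A reader might infer that the stated 5% no longer holds. For the SAP's test with 24 analysed and up to 3 missing, it does: the extreme is 0.037. Higher figures need a cut-off of 19/24, which is in neither document, or a further 1 to 3 losses from the 21, which is already net of dropout. What remains is that 0.027 and 0.037 exceed the one-sided 0.025 that a two-sided 95% interval implies.
- *Rules already exist.* The derivation in SAP 11.4.1.1 and Protocol 10.4.1 and 10.4.2 do constrain the answer. But they disagree with one another for some patients, and SAP 12.4.3.2, the passage specific to missing M6 data, refers to none of them.
- *Anyone can recompute.* The SAP requires the number missing to be reported and lists response at each visit, so a reader of the listings could apply missing as failure. That does not replace a planned analysis.
- *Knowledge at the meeting is inferred.* No document says who attends or that a running response count is shown. The supported statement is only that nothing in the design conceals outcomes from those deciding.

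**Conclusion.** The point stands in this form: the main analysis of the primary endpoint has no reproducible rule for a missing M6 response, its conservative counterpart is optional, and four passages are unreconciled. With 3 missing, judgement alone can move the result from a lower bound of 48.9% to one of 62.6%. Worst-case type I error is 0.019, 0.027 and 0.037 for 1, 2 and 3 missing, against 0.013 with none.

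This rests on 24 patients in the full analysis set, 0 to 3 missing, missingness unrelated to response, and the interval test read in the sensible direction. The set may be smaller, and the cut-off moves with it: at 23 patients (cut-off 19), 3 missing all called responders gives P(X ≥ 16 | 20, 0.60) = 0.051. All these values are bounds, not predictions, and judging patients as failures would lower the error. The documents do not support saying that the 5% level is generally broken, or that the meeting will favour responders.

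**What to change.** 1. Make missing M6 = non-response a compulsory analysis. List it in SAP 11.4.1.2 and the table index, and report it beside the main result whatever the number missing.
2. Replace the open judgement in SAP 12.4.3.2 with one fixed rule, set before the M6 results are reviewed. It should reconcile Protocol 10.4.1 and 10.4.2 with SAP 11.4.1.1 and 12.4.3.2, and state how loss after an earlier response and loss after toxicity are each coded.
3. Keep clinically judged and observed-case results as labelled sensitivity analyses.

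The first change needs only SAP wording and one more table; its cost is a less favourable figure in print if patients are missing. The second may also need a protocol clarification.

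Whether missing = non-response should be the main rule is for the sponsor to weigh. It appears to conflict with Protocol 10.4.1 for patients who respond and are then lost, and it is costly. At a true 85% with 10% missing at random, the effective rate is 0.85 × 0.90 = 0.765, and P(X ≥ 20 | 24, 0.765) = 0.30, against 0.71 with none missing.
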